4.7 Participation and Retention Strategies

Individual patient follow-up is approximately 8 years after enrollment, regardless of discontinuation of Cimzia or other medications.

As a means to retain patient participation, patients are followed up directly via a web-based system or if preferred, by mail (including a prepaid self-addressed return envelope) or by the phone every 3 months throughout the study (unless the patient withdraws consent or is deemed lost to follow-up) to complete a patient survey. “Lost to follow-up” is defined as a patient who goes 2 years with no data being collected/reported (2 years without Investigator visit/telephone contact or failure to at least partially complete 8 consecutive quarterly patient surveys; further attempts at patient contact are not required). The patients will receive emails or postal mail reminding them to complete the survey. If they have not completed the survey one week after the due date, they will be called by the independent patient interview service to complete the survey via phone. Patients completing the quarterly surveys will receive a nominal appreciation gift (if approved by the site’s IRB).

In the event an Investigator retires, or discontinues participation from the registry, the following transition plan is in place to enable continuing participation of their patients. The Informed Consent Form include wording explaining that if the patient’s Investigator discontinues participation in the registry, or retires, the independent patient interview service will be notified and the name and contact information of the closest participating study Investigator that they can contact during the remainder of their participation in the registry. The new Investigator and the patient should document re-consent of the transition. The registry can continue to collect the direct patient-reported data without the need for re-consent. If the patient is unable or unwilling to be followed by a new Investigator, the patient must be discontinued from the study.

In the event a patient moves to a new location or chooses to leave their current Investigator, patients are provided with information upon enrollment as to how to locate a participating Investigator in their area or how to provide the registry information to a new Investigator that may not yet be participating. Participating patients will have access to all of this information on the study specific web portal.

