5.4 Adverse Event Reporting to the Registry

Serious adverse events and AEs of interest are the focus of this registry; Investigators are expected to enter all SAEs and AEs of interest in the eCRF.

All SAEs and all AEs of interest will be entered in the EDC system within 24 hours of site notification and will be automatically forwarded to PRA, International for assessment and further processing as per regulatory requirements and UCB procedures (see [Figure 5-1](#), Event Reporting Process for flow of activity).

Any major changes in health status reported by the patient during the every 3 month patient follow-up will be sent to the Investigator for medical confirmation. Once medical confirmation is obtained, the Investigator will report the event through the EDC system.

To ensure the capture of any events that might occur between patient or Investigator data entry intervals, each patient will be provided a safety reporting process patient card that they

can present to an Investigator if they have an event. The card will contain instructions for the Investigator on how to report event information.

Information and instructions informing patients about the Follow-Up Period and how to report AEs is included in the Informed Consent Form. More detailed instructions to sites regarding reporting of SAEs and AEs of interest are provided in the UCB safety Guidance booklet.

[figure not shown]

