6.4 Statistical Analyses

All analyses will be performed on the eligible population, defined as all patients enrolled in this non-interventional study that meet eligibility requirements. All data captured from enrollment to last completed follow-up (Investigator or direct-to-patient) will be included.

Specifics to the primary and secondary analyses are outlined below and described in more detail in the SAP. All statistical analyses will be conducted using SAS version 9.1.3 or higher.

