3.2.1.1 Person-time at risk calculations for malignancy

Due to the long latency of malignancy, gaps in exposure between treatments will be attributed to the most recent, previous treatment. Gaps in exposure before first known treatment will not be factored into person-time calculations for these events. Any patient exposed to Cimzia during the study will only contribute person-time to the Cimzia cohort from that point onward (Figure 1). As an example, if a malignancy should occur any time after Cimzia exposure (including when Cimzia was known to be used prior to enrollment), it will be attributed to Cimzia. If a malignancy occurred in a patient prior to Cimzia exposure or in a patient with no Cimzia exposure, then it would be attributed to comparator. Thus, a patient may have exposure to multiple comparator drugs, but any malignancies diagnosed after treatment with Cimzia would be systematically attributed to Cimzia, even after ending or switching from Cimzia.

Figure 1: Example person-time at risk for malignancy events

Exposure person-time at risk will be calculated for each CD treatment using the following equation:

$$\text{Last Date} - \text{First Date} + 1$$

where all person-time is contributed to Cimzia after first Cimzia dose is administered.

First date is defined as the latest enrollment date or first CD treatment date after enrollment (whichever is later) or first Cimzia dose date if switching from a comparator treatment after enrollment. Last date is defined as the earliest of the following:

- Date of safety event of interest (for incidence rate calculations only)

- Date of discontinuation, withdrawal, or data cutoff

See Section 11.1, appendix 1 for more examples of treatment allocation scenarios for malignancies.

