3.2.1.2 Person-time at risk calculations for acute events

Exposure person-time at risk will be calculated for each CD treatment using the following equation:

$$\text{Last Date} - \text{First Date} + 1$$

First date is defined as the latest enrollment date or first CD treatment date after enrollment (whichever is later) or the first dose of new treatment if switching treatments. Last date is defined as the earliest of the following:

- Date of safety event of interest (for incidence rate calculations only)
- Last dose date + treatment class-specific half-life exposure for product
- Date of discontinuation, withdrawal, or data cutoff

Any gaps in exposure, as illustrated in the figure below, will be included in the gap treatment group person-time at risk calculations for acute events. Any overlap in treatment groups will be included in the overlap group person-time at risk calculations for acute events.

Figure 2: Example person-time at risk for acute events

[figure not shown]

Figure 2 presents an example of a patient's exposure history. For this example, exposure person-time at risk would be calculated as follows:

Exposure person-time = (Last treatment date + Treatment class-specific half-life) – First treatment date + 1) + (earliest of End treatment date + treatment class-specific half-life exposure, last date in study, data cutoff date) – Resume treatment date + 1).

See Section 11.1, appendix 1 for more examples of treatment allocation scenarios for acute events.

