3.5.2 Full Analysis Set

All analyses will be conducted on the Full Analysis Set, defined as all patients enrolled in this non-interventional study that meet eligibility requirements. All data captured from enrollment to last completed follow-up (physician or direct-to-patient) will be included.

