8.2.2 Adverse Events

Any event reported by the investigator or found in the drug safety database excerpt is considered an adverse event. Investigator and drug safety AEs have been reconciled by the study physician to avoid over reporting.

When an AE is considered serious in either source, it is treated as serious in the analysis and the related coding data is used.

Events reported in the patient survey are not considered confirmed AEs and are excluded from the analysis.

AE tabulations will be done using malignancy rules (for malignancies) separately using acute event rules (all AEs) unless otherwise specified.

A summary of study-emergent AEs, including the number of events reported, the number and percentage of patients reporting at least one AE, the number and percentage of patients reporting at least one AE of Interest, the number and percentage of patients with at least one serious AE (SAE), and the number and percentage of deaths will be presented. In addition, the number and percentage of patients reporting at least one study-emergent treatment-related AE, the number and percentage of patients reporting at least one study-emergent treatment-related AE of Interest, and the number and percentage of patients with at least one study-emergent treatment-related SAE will also be reported. AE summaries will be produced on the enrolled cohort as well as the malignancy/acute event rules.

Study-emergent AEs are those which first occur or increase in relationship to treatment after the first dose of any CD drug following enrollment.

A breakdown of the number and percentage of patients reporting each AE as well as the number of AEs, categorized by SOC, HLT, and PT coded according to MedDRA, will be presented. Note that patients are only counted once within each SOC, HLT, or PT. Uncoded AEs will be summarized in unknown SOC, HLT and PT. This will be produced for the enrolled cohort as well as both the malignancy and acute event rules.

A further tabulation of these data, broken down by relationship to treatment, will be presented. Patients with multiple events within a particular body system or preferred term will be counted under the category of their most drug-related event within that SOC, HLT or PT. Relationship to treatment is categorized as related or not related as collected on the eCRF.

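### Person-time can continue on patient surveys alone while unconfirmed survey events are excluded, so event capture falls by an unmeasured amount, mainly for malignancy

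*SAP*

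**What the plan says.** **Events that count.** SAP 8.2.2 defines the numerator by two sources: "Any event reported by the investigator or found in the drug safety database excerpt is considered an adverse event". It then says of the surveys: "Events reported in the patient survey are not considered confirmed AEs and are excluded from the analysis". The same section leaves survey data out of the AE listing. Protocol 5.4 gives the route from a survey to the numerator. A health change reported by the patient is sent to the investigator, and "Once medical confirmation is obtained, the Investigator will report the event through the EDC system".

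**Time that counts.** Protocol 6.4 and SAP 3.5.2 accept data from either source; the SAP wording is "All data captured from enrollment to last completed follow-up (physician or direct-to-patient) will be included". For malignancy, SAP 3.2.1.1 ends person-time at the event or at the "Date of discontinuation, withdrawal, or data cutoff". SAP 3.2.1.2 adds one more stop for acute events: "Last dose date + treatment class-specific half-life exposure for product". Neither list mentions last investigator contact.

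**Loss to follow-up.** Protocol 4.7 names two triggers: 2 years with no investigator visit or call, or eight quarterly surveys in a row not even partly completed. SAP 2.3.2 keeps only the survey trigger.

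**Contact with investigators.** Protocol 4.5 makes no visit mandatory. If an investigator leaves, Protocol 4.7 says "The registry can continue to collect the direct patient-reported data without the need for re-consent", and adds that a patient who cannot or will not move to a new investigator has to be discontinued.

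**The concern.** The denominator accepts follow-up from two sources. The numerator does not accept events from one of them unless someone else confirms them. A patient who keeps answering surveys but has stopped seeing an investigator goes on adding person-years in which an event is less likely to be counted.

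Malignancy is the most exposed outcome. Its time is not cut at the end of an exposure window, and it stays with Cimzia after Cimzia is stopped or switched (SAP 3.2.1.1 and 3.6). Long post-treatment periods therefore depend on continued capture. Acute events are less exposed, because their time ends with the exposure window and gap time sits in a separate group outside the comparisons in SAP 8.1.3. Surveys also collect exposure every quarter (Protocol 4.8.2), so survey-reported dosing may still extend acute-event time.

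What is at stake is the absolute rates, which would be too low, and the between-group ratio if the shortfall is unequal. Protocol 4.5 introduced the surveys to limit missing data and unreported events. The SAP neither counts the unconfirmed survey reports nor tests their effect.

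**Working it through.** The plan gives no figure for time without investigator contact, so there is none to reproduce. Its only person-time figure, about 25,000 patient-years (Protocol 6.3, SAP 2.4), does not enter this point. Current inputs give 3045 × 5.838 = 17,777 patient-years (mean derived in step 3); that mismatch is a separate matter.

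**1. The rules side by side**

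| Situation | Does time continue? | Can an event count? |
|---|---|---|
| Investigator contact continues | Yes | Yes |
| Surveys only, investigator still active | Yes; the SAP sets no limit while surveys are answered | If the investigator confirms a forwarded report, another physician reports through the patient card, or it is in the safety database excerpt |
| Investigator gone, patient takes no new one | No; patient is to be discontinued (Protocol 4.7) | Not applicable |

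The gap is the second row.

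**2. Effect on rates and ratio**

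Let f be the share of a group's person-years without investigator contact, and c the share of true events in that time that still reach the numerator. Both are assumptions. Assume also the same true rate in both kinds of time, and full capture while contact continues.

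Observed rate / true rate = 1 − f(1 − c)

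| f | c = 0 (worst case) | c = 0.5 |
|---|---|---|
| 0.05 | 0.95 | 0.975 |
| 0.10 | 0.90 | 0.95 |
| 0.20 | 0.80 | 0.90 |
| 0.30 | 0.70 | 0.85 |

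Observed ratio / true ratio = [1 − f(1 − c)] for Cimzia ÷ [1 − f(1 − c)] for comparator

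| Cimzia f, c | Comparator f, c | Multiplier of the ratio |
|---|---|---|
| 0.10, 0 | 0.10, 0 | 0.90/0.90 = 1.00 |
| 0.10, 0 | 0.20, 0 | 0.90/0.80 = 1.125 |
| 0.20, 0 | 0.10, 0 | 0.80/0.90 = 0.889 |
| 0.20, 0.5 | 0.20, 0 | 0.90/0.80 = 1.125 |

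The last row shows that equal silent time does not protect the ratio if capture differs. Protocol 5.6 makes that possible. It ties inclusion in the sponsor's safety database to 70 days from the last Cimzia dose, with malignancy, death and pregnancy also included later. It describes no matching rule for acute events in patients never given Cimzia.

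**3. How long silent time can last**

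Under the protocol's investigator-contact trigger, one silent spell lasts at most about 2 years. With 8% annual loss over 8 years, mean follow-up is (1 − 0.92^8)/(−ln 0.92) = 0.4868/0.08338 = 5.84 years. If a share u of patients each had one 2-year silent spell, the silent share of person-years would be roughly 2u/5.84:

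- u = 10%: 3.4%
- u = 20%: 6.9%
- u = 30%: 10.3%
- u = 50%: 17.1%

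Under the survey-only rule in SAP 2.3.2, a spell could in principle approach the full 8 years.

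**4. Precision**

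A rate ratio of 1.5 needs 4(1.960 + 0.842)²/(ln 1.5)² = 191 events for 80% power (equal groups, two-sided 0.05). Losing 10% or 20% of events equally in both groups lowers power to about 76% or 71%. The SAP calls its analyses descriptive, so this is secondary.

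**The case against.** The strongest reply is that the documents contain several safeguards.

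- The drug safety database is a second numerator source. A reader might infer that no event can count in survey-only time; the opening sentence of SAP 8.2.2 rules that out. Forwarded survey reports can also be confirmed, telephone contact is allowed (Protocol 4.5), and the patient card lets another physician report (Protocol 5.4).
- A reader might picture patients whose investigator has retired staying at risk for years. Protocol 4.7 requires a patient without a new investigator to be discontinued, which ends person-time.
- The SAP is to be read with the protocol (SAP 1), and the protocol has the 2-year investigator-contact trigger. The CRO also contacts sites or patients about data entry, with a six-month interval for investigators (Protocol 4.8.2).
- Excluding unconfirmed reports fits the protocol's case definitions, which require tissue confirmation for malignancy (Protocol 5.2.4).
- The silent share is assumed, and nothing shows that such patients are numerous.

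Most of this stands and limits the point to reduced capture. It does not close the gap. The discontinuation rule does not reach a patient who stops attending an investigator who is still active. Protocol 5.6 describes the safety database as receiving events collected from the registry, so its independence from investigator reports is unclear. Death and cancer registries are searched (Protocol 4.7), but no text brings matches into the AE analysis, and data-warehouse output is not used to seek further events from investigators. Reading the SAP with the protocol does not settle which loss-to-follow-up rule governs person-time.

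**Conclusion.** The point holds as reduced and unmeasured capture during time without investigator contact, chiefly for malignancy. Absolute rates are biased low by f(1 − c): at most 10% if f is 0.10, and less to the extent that other routes work. The ratio is unaffected if f and c are equal in both groups. Otherwise it moves by factors such as 1.125 or 0.889. These sizes rest on assumed values, because the documents give neither f nor c.

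A reader might infer that the registry would look falsely reassuring for Cimzia. The documents do not support a direction. More silent time after stopping Cimzia would pull the ratio down; fuller safety-database capture of Cimzia patients would push it up. Nor do they support applying the same loss to every AE of interest, given the exposure-window stop for acute events.

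What is established is a loss-to-follow-up rule that differs between the two documents, and the absence of any analysis that would show whether the bias matters.

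**What to change.** 1. Reconcile SAP 2.3.2 with Protocol 4.7, so that person-time follows one loss-to-follow-up definition that includes the investigator-contact criterion. State the end date it implies in the Last Date lists.
2. Keep the current main analysis. Report person-years with and without investigator contact by treatment group. This measures f directly.
3. Add to SAP 3.2.1.1 and 3.2.1.2 a sensitivity analysis that ends both time and events at last investigator contact plus 6 months, the investigator reporting interval in Protocol 4.8.2.
4. Add a sensitivity analysis that counts survey-reported malignancies and hospitalised events with no investigator response, tabulated by confirmation status and group. It assumes that the survey's health-status item identifies such events; the form is not in the documents.

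The cut in item 3 should not become the main analysis. It would discard confirmed late events and late time for a long-latency outcome, and leaving an investigator may be related to health.

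Cost: SAP wording and modest programming on data already collected. Item 3 has fewer person-years and possible informative censoring. Item 4 counts unverified events.
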